4.13.7.7 Illustration of power to detect a phenotypic sieve effect

We conduct power calculations based on TZM-bl neutralization IC_{50} values (in mcg/mL) of VRC07 (a close cousin of VRC01) to approximately 100 viruses representing global HIV-1 diversity (data provided by [name], [name], and [name] from the VRC). From the control group we sample 35 HIV-1 infections with IC_{50} from the VRC07 data set, and from the pooled mAb group we sample 30 HIV-1 infections with IC_{50} values bias sampled based on IC_{50} -dependent PE, with PE(x) the probability an infected control recipient would be infected had he (or she) received the mAb with IC_{50} value of x to the exposing virus. Figure 4-12 shows power for comparing the VRC01 IC_{50} distribution of the pooled mAb group HIV-1s versus the control group HIV-1s, based on a two-sample Wilcoxon rank sum test. The effect size indexing a difference between the two groups is equivalently expressed in terms of the PE(x) function (where a horizontal line indicates the null hypothesis of no difference) or in terms of a different cumulative distribution function of the IC_{50} in the two groups. Four correlates effect sizes are considered, ranging from the weakest (Effect Size 1) to the strongest (Effect Size 4). The results show that there is moderate power to detect Effect Size 3 phenotypic sieve effects (second steepest curve in Figure 4-12, power = 0.793).

Power of Wilcoxon test (2-sided 0.05 level test)						
	Number of control cases					
PE(x)	25 30 35 40					
Effect size 4	93.9	97.1	98.6	99.4		
Effect size 3	65.1	72.8	79.3	85.4		
Effect size 2	27.2	31.0	36.9	41.1		
Effect size 1	10.2	11.1	12.5	13.8		
H ₀ : PE(x)=60%	4.7	4.9	4.9	5.0		

Figure 4-12 Power calculations for comparing IC₅₀ distributions between mAb group breakthrough HIV-1s and control group breakthrough HIV-1s, with difference equivalently

expressed in terms of the PE(x) curve or the cumulative IC_{50} distribution functions, where in the right panel the black/highest curve represents the distribution for the control group breakthrough HIV-1s.

Effect Size 3 is biologically plausible based on the following argument. Under the design alternative of 60% PE we expect a transition between full protection against the most sensitive viruses and zero protection against the most resistant viruses. Table 4-7 shows the percentage of susceptible viruses that are completely blocked by the VRC01 antibody and the percentage of viruses that are completely resistant to the antibody for each of the four specified effect sizes PE(x) in Figure 4-12. For example, for Effect Size 3, the most susceptible 11.6% of viruses are completely blocked (PE = 100%) while the most resistant 2.8% of viruses are completely resistant (PE = 0%) and there is a gradient of protection for the 85.6% of intermediate viruses between the two poles (Table 4-7). The wide range of neutralization (and Fc effector function) sensitivities of HIV-1s suggests that this range of prevention efficacies is plausible. For this effect size there is 79.3% power to detect a phenotypic sieve effect and hence a correlate of protection.

Table 4-7 Percentages of HIV-1s fully susceptible to VRC01 (PE = 100%) and fully resistant to VRC01 (PE = 0%) for the four different effect sizes studied in Figure 4-12

PE(x) Effect Size in Figure 1-16	Susceptible [PE = 100%]	Resistant $[PE = 0\%]$
Effect Size 4	41.9%	23.3%
Effect Size 3	11.6%	2.8%
Effect Size 2	1.0%	<0.1%
Effect Size 1	<0.1%	<0.1%
Null Hypothesis	NA	NA

The sieve analyses will be done including all MITT infected participants, as well as only including mAb group infected participants who received an infusion at the beginning of the 8-weekly interval during which HIV-1 infection was diagnosed.

5 Selection and withdrawal of participants

Participants will be healthy, HIV-uninfected (seronegative) adults who comprehend the purpose of the study and have provided written informed consent. Volunteers will be recruited and screened; those determined to be eligible, based on the inclusion and exclusion criteria, will be enrolled in the study. Final eligibility determination will depend on results of laboratory tests, medical history, physical examinations, and answers to self-administered and/or interview questions.

Investigators should always use good clinical judgment in considering a volunteer's overall fitness for trial participation. Some volunteers may not be appropriate for enrollment even if they meet all inclusion/exclusion criteria. Medical, psychiatric, occupational, or other conditions may make evaluation of safety and/or serum mAb concentration and efficacy difficult, and some volunteers may be poor candidates for retention.

Determination of eligibility, taking into account all inclusion and exclusion criteria, must be made within 56 days prior to enrollment unless otherwise noted in Sections 5.1 and 5.2.

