2.4.4 HIV diagnostic testing

HIV diagnostic testing will be scheduled at least every four weeks and at any time following participant report of possible exposure during the study. See Section 8 for further detail on HIV-infection assessment. Participants who are diagnosed with HIV infection after enrollment will not receive additional infusions. Infusions will also be permanently discontinued for participants who have 2 reactive HIV tests, even if subsequent testing indicated that the participant is not HIV infected.

Based on the schedule of testing, it is possible that a newly infected participant may receive an infusion of VRC01 (or Control). This does not appear to pose a safety risk for participants based on existing preclinical, clinical, and in vitro data. Specifically,

passively-infused VRC01 given to NHP on Day 7 after SHIV SF162P3 infection reduces viremia and does not cause clinical harm (see IB). Additionally, passive transfer of neutralizing antibodies (at non-protective levels) prior to infection improved control of SHIV viremia and was associated with early nAb development in infected infant macaques [72]. Furthermore, VRC01 has been evaluated in viremic and aviremic HIV-infected participants (see Section 2.9.1). VRC01 administration is associated with statistically significant transient reductions in HIV viral load in adults with chronic HIV infection (see IB), and HIV variants that escape from in vitro VRC01 neutralization have reduced viral fitness [73]. Studies evaluating VRC01 in acutely infected subjects are being initiated based on these data.

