4.6.1 Assumptions of the sample size calculations including sequential monitoring for PE

The following assumptions are made for the sample size calculations:

- 10% annual dropout incidence in each of the three study groups
- 32 month uniform accrual with halved accrual during the first three months (approximating current accrual projections)
- visits every 4 weeks for HIV-1 diagnostic tests through Week 80 and HIV-1 status at Week 80 is known
- 3% annual HIV-1 incidence in the control group

- For each of the mAb treatment groups, average PE versus control within an 8-week infusion interval is assumed to be the same for each of the 10 infusion intervals
- Sequential monitoring of the mAb groups versus control to stop early for:
 - Potential harm [Establish that PE (pooled over the mAb groups) < 0% based on a 2-sided monitoring adjusted 90% CI lying below 0%]
 - Non-efficacy [Establish that PE (pooled over the mAb groups) $\leq 40\%$ based on a 2-sided 95% nominal CI lying below 40%]
 - High efficacy [Establish that PE (pooled over the mAb groups) > 70% based on a 2-sided 95% nominal CI lying above 70%]

With the exception of the potential harm monitoring, the sequential monitoring of PE does not use critical values adjusted for the number of analyses. Examination of the design operating characteristics (reported in the figures and tables below) was used to ensure that this approach provides a fitting trade-off of the control of false negative and false positive error rates.

Justification for the incidence assumptions is provided in Section 4.6.6.

We also show power calculations allowing for lower levels of HIV-1 incidence or higher levels of dropout. In particular, we show power calculations assuming 1.65% annual HIV-1 incidence in the control group, which would account for lower than expected incidence rates due to increased PrEP usage. Similarly, power calculations based on 15% annual dropout incidence are also considered.

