7.3 Enrollment and infusion visits

Enrollment is simultaneous with first infusion. The time interval between randomization and enrollment should not exceed 4 working days. The CRS requests the randomization assignment from the Web-based randomization system. Circumstances may require a participant's enrollment visit to be changed. This may exceed the 4-day randomization time limit.

At all infusion visits, the following procedures are performed before infusion:

- Abbreviated physical examination, including weight, vital signs, and a symptomdirected evaluation by history and/or appropriate physical exam based on participant self-reported symptoms or complaints (see SSP for more detail);
- Assessment of baseline reactogenicity parameters;
- Assessment of any new or unresolved AEs/intercurrent illnesses;
- Assessment of concomitant medications (as described in Section 7.2);
- ALT;
- Creatinine;
- CBC with differential;
- Urine or serum pregnancy test (for participants who are capable of becoming pregnant). Persons who are NOT capable of becoming pregnant due to having undergone total hysterectomy or bilateral oophorectomy (verified by medical records), are not required to undergo pregnancy testing; and
- Blood collection for HIV testing, PrEP monitoring, and sample storage.

Following completion of all procedures in the preceding list, and if results indicate that infusion may proceed, infusion is administered (see Sections 6.3 and 6.4).

Administration of an infusion and infusion-related procedures must be accomplished within 1 calendar day.

Immediately following the first infusion, the participant remains in the clinic for observation and initial reactogenicity assessment. See the SSP for details regarding infusion visit protocols and subsequent infusion observation and reactogenicity assessment procedures that CRSs must follow. The site will make arrangements to obtain a report of reactogenicity events from the participant after the 3-day reactogenicity period (as described in Section 7.10 and in the SSP).

The following procedures will be performed at all infusion visits. These procedures may be performed prior to, during, or following infusion:

- Administration of the participant questionnaire which may include acceptability, behavioral risk, study product belief, motivations, and social impact domains (must be done prior to risk reduction counseling);

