⁵ Visit #.X indicates a Redraw visit where # is a Schedule 1 visit number. Confirmatory draw for HIV diagnostics will be collected at the Redraw visit, in addition to the other indicated specimens. The Redraw visit should occur as soon as possible after the clinic receives a Redraw Request from the HIV diagnostics laboratory. Multiple subsequent Redraw visits may be necessary; only the EDTA blood specimens for HIV diagnostics, viral isolation/sequencing, and plasma storage will be collected at the subsequent Redraw visits. Refer to the HIV Testing SSP for more information.

⁶ Functional humoral assays include nAb, ADCC, virion capture, and phagocytosis assays.

⁷ Date of diagnosis = date of the initial specimen draw that led to the first Redraw Request.

⁸ A 3mL volume is included in the visit totals for drawing a non-additive discard tube to prevent blood tube additive cross-contamination. Refer to the Specimen Collection SSP for more information.

Appendix H Schedule 3—Laboratory procedures for participants discovered to have been HIV-1–infected at enrollment or who become HIV-2–infected

				Visit:	#.X ⁵	Visit:	47	48	
						Days:	D28	D168	
						Weeks after diagnosis ⁷ :	W4	W24	
Procedure	Ship to ¹	Assay location ²	Tube Type ³	Tube size (vol. capacity) ³					Total
BLOOD COLLECTION									
Screening or diagnostic assays									
HIV diagnostics	UW-VSL / Peru CTU Laboratory / CADIG-Immunodiagnostic Lab (INI-FIOCRUZ)	UW-VSL / Peru CTU Laboratory/ CADIG-Immunodiagnostic Lab (INI-FIOCRUZ)	EDTA	10mL	20		_	_	20
HIVPCR viral load	UW-VSL / Peru CTU Laboratory / CADIG-Immunodiagnostic Lab (INI-FIOCRUZ)	UW-VSL / Peru CTU Laboratory/ CADIG-Immunodiagnostic Lab (INI-FIOCRUZ)	EDTA	10mL	—		10	10	20
CD4+T cell count	Local Lab	Local Lab	EDTA	5mL	5		5	5	15
Drug levels									
VRC01 Ab levels	CSR	NVITAL	SST	8.5mL	8.5			_	8.5
Immunogenicity & Virologic Assay	/S								
Functional humoral assays ⁶	CSR	HVTN Labs / VRC / NVITAL	SST	8.5mL	17		_	—	17
Viral isolation/sequencing	CSR	TBD	EDTA	10mL	10		_	—	10
Storage									
Serum	CSR		SST	8.5mL	25.5		17	17	59.5
Plasma	CSR		EDTA	5mL	5			_	5
PBMC	CSR		ACD	8.5mL	34		_	-	34
Visit total ⁸	-				128		35	35	198
56-Day total					128		163	35	
URINE COLLECTION									
Pregnancy Test ^₄	Local Lab	Local Lab			х			—	

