## 5.4 Estimated Date of HIV-1 Infection

For all participants diagnosed with HIV-1 infection, the sample available at the nearest date before the diagnosis date will be tested using HIV-specific PCR. If it is positive, then the sample at the second nearest date before the diagnosis date will be tested using HIV-specific PCR. This 'look-back' procedure will be repeated until an HIV-specific PCR negative test result is obtained or until a test is done for a Day 0 sample. The complete HIV diagnostic test history including retrospective testing is used to estimate the date of infection as described in detail in Section 4.2 of the Correlates of Prevention Efficacy SAP. The estimated infection

date will be used as the event-date for secondary analyses of Primary Endpoint 2 that analyze time since last infusion received prior to the estimated infection date as well as for marker correlates and sieve analyses of breakthrough HIV-1 infections (see the Correlates of Prevention Efficacy SAP for details) and may also be used for exploratory analyses of the primary efficacy endpoint. The estimator for the date of HIV-1 infection may be refined to be based on additional data beyond the diagnostic testing information (details of this estimator are described in the Correlates of Prevention Efficacy SAP).

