**Table 5A. Visit Retention by Treatment Assignment**

	Total	A	B	C
Total Enrolled	xxx	xxx	xxx	xxx
Week 4 / 28 days post Infusion 1				
Expected and/or Completed visit	xxx (xx.x%)	xxx (xx.x%)	xxx (xx.x%)	xxx (xx.x%)
Retained	xxx (xx.x%)	xxx (xx.x%)	xxx (xx.x%)	xxx (xx.x%)
Missed visit	xxx (xx.x%)	xxx (xx.x%)	xxx (xx.x%)	xxx (xx.x%)
Terminated	xxx (xx.x%)	xxx (xx.x%)	xxx (xx.x%)	xxx (xx.x%)
Permanently discontinued infusion	xxx (xx.x%)	xxx (xx.x%)	xxx (xx.x%)	xxx (xx.x%)
Week 92 / 140 days Post Infusion 10				
Expected and/or Completed visit	xxx (xx.x%)	xxx (xx.x%)	xxx (xx.x%)	xxx (xx.x%)
Retained	xxx (xx.x%)	xxx (xx.x%)	xxx (xx.x%)	xxx (xx.x%)
Missed visit	xxx (xx.x%)	xxx (xx.x%)	xxx (xx.x%)	xxx (xx.x%)
Terminated	xxx (xx.x%)	xxx (xx.x%)	xxx (xx.x%)	xxx (xx.x%)
Permanently discontinued infusion	xxx (xx.x%)	xxx (xx.x%)	xxx (xx.x%)	xxx (xx.x%)

Post-infusion visits are not expected if the infusion visit was not done.

Retention = # Participants who completed the visit / # Participants expected for and/or completed the visit.

A visit is considered expected if the participant is in Schedule 1 at the time of the visit and the visit window has closed.

A visit is considered completed once the Post-Enrollment IV Infusion Administration or Specimen Collection form is entered in the study database.

**HVTNxxx/HPTNxxx:  
 Closed DSMB Report for DSMB meeting on [Date].  
 Data Cutoff date:[Date].**

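### The supportive on-infusion sieve analysis judges infusion status at the interval of diagnosis, not of infection, and restricts only the mAb cases

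*Protocol*

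**What the plan says.** The last paragraph of Protocol 4.13.7.7 plans the sieve analyses twice. The first version is unrestricted: "The sieve analyses will be done including all MITT infected participants". The second is limited, "only including mAb group infected participants who received an infusion at the beginning of the 8-weekly interval during which HIV-1 infection was diagnosed". No matching limit is stated for control cases. The natural reading is that all of them stay in as the comparator. Taken strictly literally, the second version would contain no control cases and so no contrast.

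Other provisions bear on this:

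- **Diagnosis date.** Protocol Appendix G: "Date of diagnosis = date of the initial specimen draw that led to the first Redraw Request". Under SAP 5.3, later PCR testing of earlier stored samples does not move it.
- **Infection date.** SAP 5.4 estimates an infection date from the full test history, including look-back PCR. It assigns that date to analyses of time since last infusion, "as well as for marker correlates and sieve analyses of breakthrough HIV-1 infections". Details are left to the separate Correlates of Prevention Efficacy SAP.
- **Order of events.** Protocol 7.3: "At all infusion visits, the following procedures are performed before infusion". The HIV blood draw is on that list. Appendix J does not require the HIV result before infusing, and Protocol 2.4.4 accepts that a newly infected person may be infused.
- **Interval boundaries.** Protocol 4.13.7.3 divides the infusion intervals into weeks 1-4 and 5-8, and so on to 73-76 and 77-80. Protocol 4.9.2 and SAP 9.1 count the first four as Weeks 1 through 32.
- **Control arm.** Blinded saline infusions on the same 8-weekly schedule (Protocol 2.4.2, 2.4.3, 4.12).

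**The concern.** The second analysis exists to isolate breakthroughs that occurred while antibody was on board, as evidence for secondary objective 1. Two features work against that.

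**Timing.** Antibody matters when the virus is acquired, but the rule looks at the interval of diagnosis. Take a participant who misses the Week 24 infusion, is infected at Week 31, tests negative at Week 32, is infused that day and is diagnosed at Week 36. This case is kept, although the interval of infection had no infusion. Now take a participant infused at Week 24 and infected at Week 31, who misses the Week 32 infusion and is diagnosed at Week 36. This case is dropped, although the interval of infection did have one.

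**Arms.** A sieve analysis contrasts mAb with control viruses. If only the mAb side is selected on adherence, anything that is related to both adherence and the circulating viruses (country or site, say) enters the contrast. It could create or mask a difference without any VRC01 effect.

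**Working it through.** **1. Number of cases.** Use the competing-exponential form of SAP 9.4.2.1 with the Protocol 4.6.1 inputs (3% control incidence, 10% dropout) and PE = 60%: N × p × [1 − exp(−(p + d) × 80/52)] / (p + d).

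- Control: 900 × 0.03 × [1 − exp(−0.13 × 80/52)] / 0.13 = 37.6. Table 4-3 has 37.
- mAb: 1800 × 0.012 × [1 − exp(−0.112 × 80/52)] / 0.112 = 30.5. Table 4-3 has 30.

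**2. Which interval owns an infusion-visit draw.** Weeks 25-32 form one interval, so a Week 32 draw closes the interval opened by the Week 24 infusion. The Week 80 visit has a draw and no infusion, which fits only this convention. A person who misses Week 24 and is positive on the Week 32 draw is therefore correctly excluded, even if infused that day.

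**3. How errors then arise.** The draw precedes the infusion, so an infusion at the start of an interval implies a test at that visit. Wrongly keeping a case therefore needs an infection not yet detectable on that test. Wrongly dropping a case can come from the same lag, or from a missed infusion visit. SAP Appendix A, Table 5A notes: "Post-infusion visits are not expected if the infusion visit was not done". After a missed infusion visit the next scheduled test may thus be a full interval away.

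**4. Share diagnosed one interval late.** Protocol 4.6.1 assumes "visits every 4 weeks for HIV-1 diagnostic tests through Week 80". Let infection be uniform over the 8 weeks, tests fall at weeks 4 and 8, and detection lag be w weeks (0 to 3, an assumption; the documents give no figure). Diagnosis moves to the next interval with probability f = w/8.

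**5. Effect on infusion status.** Let each infusion be missed independently with probability m, from 10% to 30% (the 90% target and 70% minimum of SAP 9.5). A case is misclassified when the two adjacent infusions differ: f × 2m(1 − m). Among cases kept, the share infected in an interval with no infusion is f × m(1 − m)/(1 − m) = f × m.

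| Lag w (weeks) | Diagnosed in next interval | Misclassified, m = 10% to 30% | Off infusion among kept |
|---|---|---|---|
| 0 | 0% | 0% | 0% |
| 1 | 12.5% | 2.25% to 5.25% | 1.25% to 3.75% |
| 2 | 25% | 4.5% to 10.5% | 2.5% to 7.5% |
| 3 | 37.5% | 6.75% to 15.75% | 3.75% to 11.25% |

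A simulation of 1,000,000 infections with the first infusion always given yields, at 2 weeks, 4.3% to 10.2% misclassified and 2.2% to 6.5% off infusion among those kept. Of 30 mAb cases, 30 × 0.043 = 1.3 to 30 × 0.102 = 3.1 are misclassified.

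**6. Sensitivity to hazard.** Step 5 gives infection the same hazard on and off infusion. If the hazard off infusion were 1/0.4 = 2.5 times as high, the share of infections acquired off infusion would be q = 2.5m/(2.5m + 1 − m). The off-infusion share among those kept at a 2-week lag becomes q·f(1 − m) / {q·f(1 − m) + (1 − q)[1 − f·m]}, which is 6.0% at m = 10% and 16.9% at m = 30%. This assumes no residual protection after a missed dose.

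**7. Residual antibody.** Start from the 8-week troughs in Protocol 2.9.3 (4.6 and 9 mcg/mL for 10 and 30 mg/kg) and the 15-day half-life in 2.9.2. Twelve weeks after a dose: 4.6 × 0.5^(28/15) = 1.3 and 9 × 0.5^(28/15) = 2.5 mcg/mL. At 16 weeks (56 days past the trough): 0.35 and 0.68.

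**8. One-arm selection.** As an illustration, 35 control and 30 mAb cases came from two equal strata that differed in both virus sensitivity and adherence, with no sieve effect. Under the mAb-only restriction the nominal 5% Wilcoxon test rejected in 5% to 6% of runs with adherence of 90% against 70%, and in 5% to 10% with 90% against 50%. With the same restriction in both arms it rejected in 4% to 5%.

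**The case against.** Four arguments weigh against the point.

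- **The interval convention already excludes the obvious bad case.** A reader might infer that a Week 32 draw belongs to the interval that the Week 32 infusion opens. The late share would then be (4 + w)/8, or 75% at a 2-week lag, with 13% to 31% misclassified. Protocol 4.13.7.3 and 4.9.2 and SAP 9.1 do not support that reading, and those figures should not be used. This argument stands in full; only the smaller figures above remain.
- **The timing may be settled elsewhere.** SAP 2.2 places all secondary objective 1 analyses in the Correlates SAP, which was not available for this review, and SAP 5.4 already names the estimated infection date. This stands as a limit on certainty, but the Protocol sentence remains unreconciled with SAP 5.4.
- **Control infusions are saline.** Receiving one has no antibody meaning, and all control viruses can represent the exposing viruses. No document links adherence to virus sensitivity, so the bias is hypothetical. That is fair on size. But blinding and the common schedule make the same selection available in the control arm, and the per-protocol Cox analysis in SAP 8.2, repeated for sensitive viruses under 8.3.2, does not limit its adherence rule to one arm.
- **Restricting controls costs power and still leaves a post-randomisation subset.** Both parts are true. They argue for labelling the analysis supportive, not for selecting in one arm only.

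**Conclusion.** The point holds as a modest defect in a supportive analysis. At an assumed 2-week lag and 10% to 30% missed infusions, about 1 to 3 of 30 mAb cases are misclassified and about 2% to 7% of those kept were off infusion when infected. These figures rest on the assumed lag, uniform infection times, independent missed infusions and equal hazard on and off infusion. They fall to zero with no lag and no missed tests, and rise if infections concentrate in missed intervals. The distortion from one-arm selection cannot be sized from the documents.

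Two stronger conclusions might be drawn, and neither is supported. One is that the sieve evidence as a whole loses its randomised comparison; the all-MITT version in the same sentence is untouched. The other is that the wrongly kept viruses never met VRC01; every enrolled participant receives the first infusion (Protocol 4.13.3), and the levels in step 7 are low, not absent.

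**What to change.** Keep the all-MITT sieve analysis as the main one. Restate the second along these lines: *a supportive analysis, in a post-randomisation subset, will include infected participants of all three arms who received the scheduled infusion that opened the 8-week interval containing the estimated date of HIV-1 infection (SAP 5.4).* Confirm that the Correlates SAP says the same.

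No new data are needed: SAP 5.4 already plans the dates, and infusions are recorded in every arm. Off-infusion cases then drop out by definition, apart from error in the estimated date.

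The cost falls on this analysis alone. About 0.9 × 37 = 33 control cases remain at 90% adherence and 0.7 × 37 = 26 at 70%. As a guide, the table in Figure 4-12 gives Effect Size 3 power of 79.3%, 72.8% and 65.1% with 35, 30 and 25 control cases, so the loss at low adherence is real. mAb cases (about 27 of 30, or 21 of 30, with equal hazard) are lost under either rule.
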